Objective 1: Evaluate effectiveness and implementation of the Tele-Savvy intervention, a group-based, remotely delivered psychoeducational intervention for family and other informal caregivers of older adults with Alzheimer's disease and related dementia (ADRD). In this pilot pragmatic clinical trial, we will introduce the Tele-Savvy intervention to ADRD caregivers at two health care system sites—UConn Health and Emory Healthcare—to determine feasibility and acceptability of offering Tele-Savvy as a routinely available caregiver program at both health care systems. To evaluate effectiveness, at each study site, we will conduct three sequential 7-week Tele-Savvy programs with 10 caregivers in each program. Caregivers will be randomly assigned to participate in either the Tele-Savvy Program or a self-guided Caregiving During Crisis program. To evaluate implementation, we will use Normalization Process Theory as a guide, with the goal of understanding staff acceptability and willingness to adopt Tele-Savvy as a routinely-offered caregiver psychoeducational program.

Objective 2: Establish an identification and invitation strategy, embedded into the daily workflow of both study sites, enabling caregivers to be invited to participate in the Tele-Savvy program in a pragmatic fashion. We will use electronic health records (EHRs) to identify family members or significant others linked to patients with diagnoses of ADRD, and then verify the accuracy of these identified individuals by having clinicians confirm or disagree with these identified individuals.. These identified individuals will be invited to participate either via electronic means or by clinic staff members.

Objective 3: Demonstrate viable routine collection of caregiver outcomes data into EHRs. Collaborating with information technology and clinical personnel at both health care systems, we will implement procedures enabling routine collection of these caregiver measures and inclusion of these measures into the EHRs at both health care systems.

Design and Outcomes

This cluster randomized pragmatic clinical trial will test the effectiveness and feasibility of embedding the Tele-Savvy intervention, a psychoeducational program for family and other informal caregivers of older adults living in the community with Alzheimer's disease and related dementia (ADRD), in two health care systems/clinical sites: UConn Health in Farmington, Connecticut, and Emory Healthcare in Atlanta, Georgia. A total of 100 caregivers, 50 at each study site, will participate in this pilot study. At each site, 30 caregivers will be randomly assigned to receive the Tele-Savvy intervention, and 20 caregivers will be randomly assigned to receive the self-guided Caregiving During Crisis online program.

All 100 caregivers will complete identical self-administered questionnaires to measure the caregiver-specific outcome measures in this pilot study. Outcome measures will include caregiver mastery (primary outcome), caregiver response to specific memory and behavioral

problems, and caregiver stress. Also, we will employ process measures of participation and engagement in the interventions for caregivers in both arms of the trial, as well as implementation outcomes via surveys with clinicians and Information Technology staff at each of the two clinical sites responsible for programming electronic medical records to enable capture and storage of caregiver outcomes.

Interventions and Duration

The Tele-Savvy intervention is grounded in social learning and stress process theory. Its main goal is to produce improved caregiver mastery over the symptom management skills commonly encountered when supervising and caring at home for an older adult living with ADRD. Over the 7-week program, there are synchronous and asynchronous activities each week. The synchronous portion includes weekly scheduled videoconferences (60-80 min) that serve as an online classroom in which facilitators lead lectures and discussions and provide a venue for caregivers' interactions and sharing of their experiences. The majority of Tele-Savvy is asynchronous. Daily, caregivers access online 6- to 15-min prerecorded videos, each focused on one main learning objective.

Tele-Savvy is a psychoeducation program designed to build not only knowledge and skill but also confidence. The psychoeducation approach uses three main strategies to accomplish this goal. The first strategy is instruction, providing information that helps caregivers increase their fund of knowledge for caregiving. The second strategy involves active learning, accomplished by interactive exercises conducted during the course; for example, thinking about how, given what the caregiver now understands about the cognitive losses in dementia, to best convey information to the person living with dementia. Active learning is also accomplished by asking course participants to try these strategies during the regular course of home caregiving -- this is what we refer to as "homework" -- the real life application of what is taught in class in the home setting. The third approach involves acknowledging caregiving success through a process of reporting back on caregiving activities during the week, particularly those that involved trying out the caregiving strategies taught in class. Reporting success and observing the caregiving successes of other participants is an important means of building and reinforcing caregiver confidence and competence.

The attention control group will receive the self-guided Caregiving During Crisis program. Caregiving During Crisis is a fully online, asynchronous, professionally designed continuing education course aimed at developing the competency of informal caregivers of community-dwelling persons living with dementia to ensure the safety of that person and themselves during this time of the COVID-19 pandemic. The course, readily accessible by home computer or smartphone, describes methods of home infection control and prevention to create a Safe Home space, strategies for safely leaving and re-entering the home (e.g., to shop), additional strategies for safely allowing service personnel (e.g., home health aides or electricians) and select family members to enter the Safe Home space, and risk management strategies to frame decisions when/if COVID restrictions are relaxed or revoked.

Two-thirds of the 100 caregivers (the first 67 caregivers) enrolled in the study will be on study for 6 months, and one-third of the caregivers (the final 33 caregivers) will be on study for 3 months.

Sample Size and Population

We will enroll a total of 100 caregivers into this pilot study across the two clinical sites using a cluster randomized design. A total of 60 caregivers will be randomly assigned to receive the Tele-Savvy program in three sequential cohorts of 10 caregivers each at each site. A total of 40 caregivers will be randomly assigned to receive the attention control condition in three sequential cohorts of 6-7 caregivers at each site.

STUDY TEAM ROSTER

Principal Investigator: **[name]**

UConn Center on Aging, University of Connecticut School of Medicine, [name]

[contact]

Main responsibilities/Key roles: responsible for successful conduct of all study tasks at both study sites, including direct supervision of study coordinator and research data base manager, and ensuring that personnel at both clinical sites perform their duties as required to successful conduct of the study.

Co-Investigator: **[name]**

UConn Center on Aging, University of Connecticut School of Medicine, [name]

[contact]

Main responsibilities/Key roles: Clinical lead at UConn Health site; responsible for facilitating use and modification of electronic health record system at this clinical site to enable recruitment of study participants (caregivers) and capture and storage of caregiver outcomes data in the electronic record system.

Co-Investigator: **[name]**

Nell Hodgson Woodruff School of Nursing, Emory University, [name]

[contact]

Main responsibilities/Key roles: Scientific lead at Emory site, [name] will provide training of the Tele-Savvy facilitators at both the UConn Health (Geriatrics Associates) and Emory Healthcare (IMCC) sites, ensuring that they are certified to lead both synchronous and asynchronous components independently before the first caregiver cohort begins the program. Throughout the portion of the pilot study during which Tele-Savvy classes are held, he will provide guidance and oversight at both study sites to ensure that Tele-Savvy implementation there follows study protocol.

Co-Investigator: **[name]**

[contact]

1 STUDY OBJECTIVES

This study consists of three objectives, all of which are of equal importance because this is a pilot study of a pragmatic clinical trial being tested at two health care systems, also referred to as clinical sites in this protocol.

1.1 Primary Objective

Evaluate effectiveness on caregivers and implementation of Tele-Savvy to determine feasibility and acceptability of offering Tele-Savvy as a routinely available caregiver program at both health care systems. We will test the hypothesis that caregivers receiving the Tele-Savvy intervention will experience a greater improvement in caregiver mastery than the attention control group. At each health care system, we will conduct three sequential 7-week Tele-Savvy programs. Caregivers will be randomly assigned to participate in either the Tele-Savvy Program or to receive the attention control condition, a self-guided Caregiving During Crisis program. We will use Normalization Process Theory to guide our implementation evaluation, with the goal of understanding staff acceptability and willingness to adopt Tele-Savvy as a routinely-offered caregiver psychoeducational program.

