The administrative study coordinator will electronically access the appropriate study site's randomization string (strings will be generated by the study biostatistician, see Section 4.3) after a caregiver returns completed baseline assessment forms. Randomization results will reveal whether the caregiver is assigned to the Tele-Savvy program or to the attention control group. Randomization will be performed within business 3 days of receipt of completed baseline assessment forms. The administrative study coordinator will then notify the Tele-Savvy facilitator at each study site of the randomization result, and the facilitator will notify caregivers about the treatment group to which they are assigned. The statistician will provide the randomization scheme (random sorting using 10% maximum allowable deviation using PASS 2020 software⁵⁶), which will be applied after the baseline assessment. For the Tele-Savvy intervention, because 10 caregivers at each site must be assembled in order to convene a cohort, a window of up to 3 weeks will be allowed between randomization of a caregiver to that treatment group and initiation of the intervention. For the attention control group, caregivers will be permitted to access the Caregiving During Crisis program anytime beginning 3 days after randomization.

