9.5 Data Analyses

The proposed sample size is for 60 caregivers randomized to a Tele-Savvy group and 40 caregivers randomized to an attention control group with data collection at 2 primary time points (baseline and 3 months (post treatment)). This design is adequately powered at 80% power and 5% level of significance to detect medium effect sizes for the group effect (Cohen's $f=0.285$), within subject time effect ($f=0.282$) and group-by-time treatment effect ($f=0.282$) using repeated measures analysis of variance (RM-ANOVA).^{57,58} This expected effect size is supported by previously measured improvements in caregiver mastery from the "Testing Tele-Savvy" study, NIH R01AG054079. We also intend to collect an additional follow-up time point at 6 months as a measure of sustainability of the treatment for approximately 2/3 of the participants (40 in Tele-

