Savvy and 26 in attention control). For this smaller sample with a third time point we will be able to detect larger effects sizes ($f=0.350$ for group, $f=0.388$ for the time and group-by-time effects). In the “Testing Tele-Savvy” study, an effect size of $f=0.46$ was recorded for caregiver mastery improvements in active Tele-Savvy program participants. All data will be reviewed for completeness prior to analysis. All survey instruments will be scored and reliability computed prior to analysis. All measures will be assessed for normality and modeling assumptions with mathematical transformation applied as necessary prior to analysis. Multilevel mixed linear models (MLM) will be performed to utilize all data collected at each time point for all caregivers to assess changes in measures over time adjusting for attrition as needed. MLM will also adjust for the non-independence of the data collected across time nested within each subject. Post hoc pairwise comparisons between time points within subjects will be performed using Sidak error rate adjustments to control for multiple comparisons error rate inflation. Cohort number and clinical site will also be evaluated to see if any additional clustering effects are noted within each cohort or at each clinical site. Additionally, after performing an intent-to-treat (ITT) analysis, a follow-up analysis will also be conducted to see what if any additional effects were seen for subjects who were adherent versus those who weren’t, looking at the number of sessions attended for potential dose effect. The demographics of the subjects will also be evaluated as potential covariates for the statistical models. All statistical tests will be performed at 5% level of significance, with 95% confidence intervals reported for all effect sizes.

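### Caregivers are randomized within site, but the mastery effect is analysed only pooled and site only as a possible clustering effect, so the plan cannot show whether Tele-Savvy's effect differs between the two systems

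*Combined protocol and SAP*

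**What the plan says.** Section 1.1 evaluates the effect on caregivers and implementation together, "to determine feasibility and acceptability of offering Tele-Savvy as a routinely available caregiver program at both health care systems". The mastery hypothesis in 1.1 and 9.1 compares the two arms over all caregivers and does not mention site.

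The Précis fixes the numbers by site: "At each site, 30 caregivers will be randomly assigned to receive the Tele-Savvy intervention", with 20 controls per site. Section 4.3 has the biostatistician generate a separate randomization string for each site in each wave. Section 6.2.2 has the coordinator draw from the relevant site's string and then "notify the Tele-Savvy facilitator at each study site of the randomization result".

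Section 9.5 gives power only for the pooled sample, "60 caregivers randomized to a Tele-Savvy group and 40 caregivers randomized to an attention control group". It states "This design is adequately powered at 80% power and 5% level of significance" for several effects, including the "group-by-time treatment effect ($f=0.282$) using repeated measures analysis of variance (RM-ANOVA". The analysis is a mixed linear model whose stated dependence is repeated measures within a caregiver. On site it says: "Cohort number and clinical site will also be evaluated to see if any additional clustering effects are noted". No committed site term, arm-by-site contrast or site-specific estimate is planned.

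**The concern.** A clustering check asks whether scores within a site resemble each other. It does not ask whether the difference between arms is the same at UConn and Emory. If the check is a variance component, two sites give it one degree of freedom, too few for a useful estimate. If it is something else, 9.5 does not say what, or what would follow from it.

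A difference between sites is plausible here. Section 6.2.1 says Emory already offers the program as standard practice. Section 4.3 describes a memory care clinic at one system and an outpatient geriatric center at the other. Sections 6.2.2 and 7.1 read as one facilitator per site. Section 6.2.1 also says that results will go to clinicians and administrators at both systems. They would receive one average, although randomization within site already supplies a valid comparison for each system.

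**Working it through.** **Inputs.** 60:40 overall and 30:20 at each site (9.5, Précis). Two-sided 5% level (sidedness is not stated; the F test is equivalent to two-sided). Group-by-time f=0.282, group f=0.285, and an earlier-study f=0.46 (all 9.5). Effects are in SDs of change. No dropout rate is given, so 0% is used first.

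**1. The plan's own figure.** Noncentrality λ = N·f², with F on (1, 98) df.
- f=0.282: λ = 100 × 0.282² = 7.95, power 79.7%.
- f=0.285: λ = 100 × 0.285² = 8.12, power 80.6%.

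The stated 80% reproduces. With 60:40 allocation, d = f/√(0.6 × 0.4). So f=0.282 is d=0.576 and f=0.46 is d=0.939.

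**2. Pooled test when one site has no effect.** The sites are equal in size and allocation, so the pooled effect is (d + 0)/2, that is, f/2.
- f=0.282 at the working site: λ = 100 × 0.141² = 1.99, power 28.7%.
- f=0.46 at the working site: λ = 100 × 0.23² = 5.29, power 62.5%.

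This formula leaves the residual SD unchanged. In practice the unmodelled gap between sites inflates it slightly. Simulating 100,000 trials per case with an arm-plus-site model gives 28% and 61%; with arm alone, 27% and 58%. When both sites work, the formula gives 79.7% and 99.5%. With 10% to 20% dropout (assumed), the one-null-site formula values fall to 26% to 24% at f=0.282, and 58% to 53% at f=0.46.

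**3. What site-specific estimates could show.**
- One site: SE = √(1/30 + 1/20) = 0.289 SD; 95% half-width 1.96 × 0.289 = 0.57 SD.
- Between-site difference in effect: SE = √2 × 0.289 = 0.408 SD; half-width 0.80 SD.
- Pooled: SE = √(1/60 + 1/40) = 0.204 SD; half-width 0.40 SD.
- Arm-by-site test for a gap equal to the design effect: noncentrality 0.576/0.408 = 1.41 on 96 df, power about 28% to 29%. For a gap of 0.939 SD, about 62%.
- Test within a single site at the design effect: λ = 50 × 0.282² = 3.98 on (1, 48) df, power 50%.

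These estimates can describe each site. They cannot carry separate confirmatory tests.

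**4. Site as a fixed effect.** Suppose the sites differ in mean change by 0.5 or 1.0 SD (assumed) and the arm effect is d=0.576 at both. Leaving site out lowers pooled power from 80% to about 78% or 72%, and takes the actual type I error from 5% to about 4% or 3%. Entering site restores both. It is a factor the trial already randomizes by.

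**The case against.** The strongest reply is that the pooled contrast answers the hypothesis as written. In 1.1 the reference to both systems attaches to feasibility and acceptability. Those are studied through a Normalization Process Theory evaluation, with surveys of staff at each of the two sites (Précis). That is right: a reader might infer that Objective 1 requires mastery to improve at each system, and the documents do not say so. Nor do they attach a success or adoption rule to the mastery test. Section 9.1 calls enrollment the primary goal, and section 1 gives the three objectives equal importance because this is a pilot.

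A second reply is that site is not ignored, since 9.5 says it will be evaluated, and a fixed site term would fit that sentence. This stands in part: the documents do not say that site is random. But the sentence commits to no term and confines the question to clustering.

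A third is that 30:20 per site is too small. That is a reason to label the site results descriptive. It is not a reason to leave them out. A pooled primary contrast remains an ordinary choice for a two-site pilot.

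**Conclusion.** The point holds as a limit on what the planned analysis can show. A significant pooled mastery difference would establish an average over two systems, and 9.5 plans nothing that would show whether both contribute. With one site null, the pooled test would still be significant in about 28% of trials at the design effect and about 60% at f=0.46.

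A reader might infer that the trial would reach significance with close to its full power even if Tele-Savvy did nothing at one system. The documents' figures do not support that. Keeping pooled power near 80% with a null site needs an effect of about 1.15 SD (f about 0.57) at the other, larger than any effect the documents cite. On their own figures power falls from 80% to about 28%, or from 99.5% to about 60%.

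The figures rest on assumptions: caregivers treated as independent, with no extra correlation within a Tele-Savvy cohort; f expressed per SD of change; and f=0.46 read as a between-arm effect, although 9.5 reports it for active-program participants. If f=0.46 were instead on the raw-score SD, with a baseline to 3-month correlation of 0.7 (not given), the one-null-site power would be about 83%. One facilitator per site is inferred from the wording of 6.2.2 and 7.1.

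**What to change.** In 9.5:
- Keep the pooled 3-month mastery contrast as primary.
- Enter site as a prespecified fixed effect, in place of the check for clustering by site.
- Report, as descriptive only, the arm-by-site contrast at 3 months and the Tele-Savvy minus control mastery difference for UConn and for Emory, each with a 95% confidence interval, beside the pooled value.
- State that the pooled result will be worded as an average over the two systems.

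Do not add a rule that allows a claim for both systems when both site estimates point in favor. A site with no true effect gives a favorable estimate half the time. In simulated pooled-significant trials with one null site, both estimates were favorable in about 87% when the other site had the design effect, and still in about 61% when it had 1.15 SD.

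The cost is a few sentences, one term in the primary model and one in a descriptive model, with no new data. The site intervals will be wide (about ±0.57 SD), the interaction test has only about 28% power for a gap equal to the design effect, and a difference between sites could not be separated from a difference between facilitators.

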1.2 Secondary Objectives

Establish an identification and invitation strategy, embedded into the daily workflow of two health care systems, enabling caregivers to be invited to participate in the Tele-Savvy program. We will use electronic health records (EHRs) to identify family members or significant others linked to patients with diagnoses of ADRD, and then verify the accuracy of these identified individuals by having clinicians confirm or disagree with these identified individuals. These identified individuals will be invited to participate either via electronic means or by clinic staff members.

Demonstrate viable routine collection of caregiver outcomes data into EHRs.

Collaborating with clinicians and information technology personnel at both health care systems, we will implement procedures enabling routine collection of these caregiver measures and inclusion of these measures into the EHRs at both health care systems.

2 BACKGROUND AND RATIONALE

2.1 Background on Condition, Disease, or Other Primary Study Focus

Dementia, an umbrella term encompassing multiple causes of brain neurodegeneration that result in cognitive decline and development of behavioral and psychological symptoms, affected more than 50 million people worldwide in 2019; by 2050, this number will reach more than 150 million people.¹ In 2020, an estimated 5.8 million Americans live with ADRD, and more than 16 million informal caregivers, mostly family members (*hereafter, caregivers*), provide unpaid care to them.² The scope of caregiving activities varies widely, but for individual caregivers the activities often evolve in predictable fashion over the course of the dementia disease process. Caregivers must adjust to the realization that their relative or partner has a progressive neurodegenerative illness, witness cognitive and behavioral changes, gradually assume increasing responsibility for supervising and conducting instrumental and self-care related

activities of daily living, learn how to conduct medically complex tasks, coordinate services and communication with other family members, engage in advance care planning, and gatekeep the use of emergency and acute healthcare services. Caregivers of older adults with ADRD take on these responsibilities with little guidance, and many studies have shown that these caregivers provide more intense care and experience significant psychological and physical health-related consequences compared to caregivers of older adults without ADRD.^{2,3}

In the COVID-19 era, these caregiving challenges have become compounded. It is widely known that community-dwelling older adults are at highest risk for severe illness and death from COVID-19 and are also likely to face longer in-home restrictions than other segments of the population. Caregivers of older adults living at home with chronic illnesses and associated disabilities face serious challenges related to these COVID-19 restrictions, such as how to keep older adults and themselves occupied and socially engaged to avoid loneliness and social isolation, and how to manage older adults' and their own health care needs by navigating the health care system. Caregivers of older adults with ADRD are at risk for increased physical and mental health problems due to loneliness and social isolation, especially if they experience unavailability of community-based services such as respite care and if they assume greater care responsibilities due to a shortage of in-home workers.⁴ The caregiver population is ethnically and racially diverse, so the social determinants of health associated health disparities likely add to the complexity of challenges faced in the COVID-19 era.⁵ Recent publications, principally commentaries and recommendations, have focused on the need to address caregivers of community-dwelling older adults, including those with ADRD, in the midst of the COVID-19 pandemic. Recommendations have been offered regarding the potential benefits of health care providers using technology creatively to reach caregivers at home to train them about how to avoid unnecessary hospital visits and to address accumulating needs among caregivers of older adults at home in the COVID-19 pandemic, including remote assistance using technology.⁶⁻¹¹

